Impact of Nudges on Downloads of COVID-19 Exposure Notification Smartphone Apps: A Randomized

Trial

NCT05080179

Submitted 12/11/2020

CONFIDENTIAL - FOR PEER-REVIEW ONLY**Self Benefit vs. Other Benefit X Social Norm (#54102)**

Created: 12/11/2020 11:11 AM (PT)

This is an anonymized copy (without author names) of the pre-registration. It was created by the author(s) to use during peer-review. A non-anonymized version (containing author names) should be made available by the authors when the work it supports is made public.

1) Have any data been collected for this study already?

No, no data have been collected for this study yet.

2) What's the main question being asked or hypothesis being tested in this study?

How does framing the COVID-Alert PA app in terms of self-benefit vs. other-benefit, as well including information about the number of people who have downloaded the app thus far (or not), influence the decision to download the COVID-Alert PA app?

3) Describe the key dependent variable(s) specifying how they will be measured.

Our main dependent variable is the choice to click on a link to download the COVID-Alert PA app or not.

4) How many and which conditions will participants be assigned to?

Participants will be randomly assigned to one of four conditions in a 2 (Self-benefit vs. Other-Benefit) x 2 (Social Norms Present vs. Social Norms absent) design.

All participants will receive an email that says:

COVID Alert PA is the official Exposure Notification App from the Pennsylvania Department of Health. Join Penn Medicine in the fight against COVID-19 and download COVID Alert PA today!

---We will manipulate the content here---

The app uses Bluetooth to sense when one person is in close contact with another person with the app. If someone tests positive for COVID-19, and they decide to upload the information to the health department, people who have the app and who have been in contact with them will be alerted.

If you are interested in downloading the app, please click COVID Alert PA.

We appreciate you joining our efforts. Together we can beat COVID-19!

In the Other-Benefit condition, it will say: It can help you reduce your risk of unknowingly spreading the virus to your friends, family, and larger community.

In the Self-Benefit condition, it will say: It can help you determine where and when to get testing, and how to get care if you need it.

In the Social Norms Present condition, it will say: Over 600,000 Pennsylvanians have already downloaded the app! [This number may change slightly if the number of people who downloaded the app changed from the time of the preregistration and the time of the launch]

In the Social Norms Absent condition, it will not say the statement about social norms above.

Participants who do not open the initial email will receive a follow-up email.

5) Specify exactly which analyses you will conduct to examine the main question/hypothesis.

We will conduct a logistic regression predicting choice to click on the link or not from a dummy variable representing the Self-Benefit (vs. Other-Benefit) condition, the Social Norms Present (vs. Social Norms Absent) condition, and a variable representing the interaction.

We will examine if there is a 2 (Self-Benefit vs. Other-Benefit) x 2 (Social Norms Present vs. Social Norms absent) interaction. If there is not a significant interaction, we will examine if there is a main effect of Self-Benefit (vs. Other-Benefit) and Social Norms Present (vs. Social Norms Absent).

Depending on the availability of race, age, and gender demographic variables, we will also conduct the analyses above controlling for these variables.

6) Describe exactly how outliers will be defined and handled, and your precise rule(s) for excluding observations.

We will only include participants in our analysis that have opened the sent email.

7) How many observations will be collected or what will determine sample size? No need to justify decision, but be precise about exactly how the

number will be determined.

The emails will be sent to approximately 40,000 people (10,000 per condition).

8) Anything else you would like to pre-register? (e.g., secondary analyses, variables collected for exploratory purposes, unusual analyses planned?)

NA

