5. The only potential follow-up for participants would be receiving additional e-mails from the institution about COVID Alert PA

The following documents are currently attached to this item:

There are no documents attached for this item.

Deception

Does your project use deception?

No

International Research

Are you conducting research outside of the United States?

No

Analysis Plan

Descriptive statistics, two-sample t-tests for percent download between message groups

The following documents are currently attached to this item:

There are no documents attached for this item.

Data confidentiality

Paper-based records will be kept in a secure location and only be accessible to personnel involved in the study.

Computer-based files will only be made available to personnel involved in the study through the use of access privileges and passwords.

Prior to access to any study-related information, personnel will be required to sign statements agreeing to protect the security and confidentiality of identifiable information.

Wherever feasible, identifiers will be removed from study-related information.

A Certificate of Confidentiality will be obtained, because the research could place the subject at risk of criminal or civil liability or cause damage to the subject's financial standing, employability, or liability.

A waiver of documentation of consent is being requested, because the only link between the subject and the study would be the consent document and the primary risk is a breach of confidentiality. (This is not an option for FDA-regulated research.)

Precautions are in place to ensure the data is secure by using passwords and encryption, because the research involves web-based surveys.

Audio and/or video recordings will be transcribed and then destroyed to eliminate audible identification of subjects.

Subject Confidentiality

Researchers will only receive de-identified data from institutions, there is no risk to subject confidentiality

Sensitive Research Information*

Does this research involve collection of sensitive information about the subjects that should be excluded from the electronic medical record?

No

Subject Privacy

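### SAP item 5 promises main effects but names only a dummy-coded interaction model, whose factor coefficients under 0/1 coding are simple effects in half the openers

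*SAP*

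**What the plan says.** SAP item 4 describes four conditions "in a 2 (Self-benefit vs. Other-Benefit) x 2 (Social Norms Present vs. Social Norms absent) design". Item 5, which asks for the exact analyses, gives one model, a logistic regression described as "predicting choice to click on the link or not from a dummy variable representing the Self-Benefit (vs. Other-Benefit) condition". Its other two terms are the norm-message factor and the product of the two factors. The interaction is examined first. Then: "If there is not a significant interaction, we will examine if there is a main effect of Self-Benefit (vs. Other-Benefit", with the same for Social Norms.

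If demographic variables are available, "we will also conduct the analyses above controlling for these variables". Item 6 restricts the analysis set: "We will only include participants in our analysis that have opened the sent email". Item 7 gives the only sample-size figure: "The emails will be sent to approximately 40,000 people (10,000 per condition".

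Nothing else says how a main effect is to be obtained. Item 8 is marked NA. The Protocol's Analysis Plan offers only "Descriptive statistics, two-sample t-tests for percent download between message groups", which does not address the factorial structure.

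**The concern.** In a 2 x 2 design, a main effect normally means the effect of one factor averaged over the levels of the other. The one model that item 5 names does not yield that quantity when its factors are 0/1 dummies. With the interaction in the model, each factor coefficient is the effect at the reference level of the other factor. The wording suggests Other-Benefit and Social Norms Absent as the reference levels. Those are simple effects.

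Two things are at stake in the test of the main hypothesis:

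- **Precision.** If there is no true interaction, the simple and main effects are equal, but the simple effect ignores half the openers.
- **The quantity estimated.** A non-significant interaction test does not show that the interaction is absent. If a real one is missed, the coefficient answers a different question from the one asked.

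The adjusted analysis repeats the same steps and inherits the gap.

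**Working it through.** **Plan's own figure.** 4 conditions x 10,000 e-mails = 40,000, as item 7 states. The SAP gives no open rate, click rate, effect size, power or alpha. Those below are assumptions; tests are two-sided at 0.05.

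**1. What the coefficient is.** Let L(s,m) be the log odds of a click, with s = 1 for Self-Benefit and m = 1 for norm present. The unadjusted model has four parameters for four cells, so it is saturated:

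- 0/1 Self-Benefit coefficient = L(1,0) - L(0,0).
- Main effect = ½{[L(1,0) - L(0,0)] + [L(1,1) - L(0,1)]}.

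Illustration: fix the norm-absent cells at 10% and 12% and the Other-Benefit/norm-present cell at 10%. Moving the Self-Benefit/norm-present cell through 5%, 10% and 30% leaves the 0/1 coefficient at 0.2048, while the main effect goes from -0.271 to 0.102 to 0.777.

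**2. Precision, no interaction.** Each cell logit has variance v = 1/(n p(1-p)).

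- 0/1 coefficient: v00 + v10.
- Main effect: (v00 + v10 + v01 + v11)/4.

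With equal v these are 2v and v, so the SE ratio is √2 = 1.41. Equal precision would need 2 x 40,000 = 80,000 e-mails. Dividing the non-centrality by √2 gives:

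| Power, main effect | 50% | 80% | 90% | 99% |
|---|---|---|---|---|
| Power, 0/1 coefficient | 28% | 51% | 63% | 86% |

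Example: 40% open (4,000 openers per cell), 5% base click, odds ratio (OR) 1.2, so 5.94% with Self-Benefit, and no norm effect.

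- v00 = 1/(4,000 x 0.05 x 0.95) = 0.00526; v10 = 1/(4,000 x 0.0594 x 0.9406) = 0.00447.
- 0/1 coefficient: SE = √0.00974 = 0.0987, z = 0.1823/0.0987 = 1.85, power 46%.
- Main effect: SE = √(2 x 0.00974/4) = 0.0698, z = 2.61, power 74%.

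Grid of 27 scenarios (open rate 20/40/60%, base click 2/5/10%, OR 1.1/1.2/1.3):

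- The loss is 0.5 to 29 points, median 18, and at least 10 points in 19 of 27.
- If the norm message itself has OR 0.77 to 1.3, the SE ratio is 1.32 to 1.50, the largest loss 24 to 33 points and the median 14 to 21.
- At a 5% click rate in every cell, if norm-present cells have 20% fewer or more openers than 4,000, the ratio is 1.33 to 1.48.
- Centred coding and an additive refit differ by at most 0.7 points.

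**3. Missed interaction.** Take the Self-Benefit log OR as S - d/2 with the norm absent and S + d/2 with it present, where S = ln 1.2 and d = ln(interaction OR). The 0/1 coefficient targets S - d/2 and the main effect targets S. The average norm effect is set to zero, base click is 5%, there are 4,000 openers per cell, and each column rests on 100,000 simulated trials:

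| Interaction OR | 0.77 | 0.87 | 1 | 1.15 | 1.3 |
|---|---|---|---|---|---|
| Main-effect step reached | 51% | 83% | 95% | 83% | 55% |
| OR targeted by 0/1 coefficient (main effect: 1.20) | 1.37 | 1.29 | 1.20 | 1.12 | 1.05 |
| 0/1 coefficient rejects, given step reached | 82% | 69% | 45% | 24% | 13% |
| Centred or additive rejects, given step reached | 77% | 76% | 74% | 73% | 72% |

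Among trials that reach the step, the 0/1 and main-effect tests disagree in 14 to 59%. With 2,000 openers per cell the 0/1 coefficient rejects in 52.5% down to 7%, against 48 to 43% for the main effect. With 6,000 the figures are 94% down to 20%, against 91 to 88%.

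**4. Null check.** With no effects at all, rejection at the step is 3.5% (0/1), 5.0% (centred) and 4.9% (additive).

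**The case against.** The SAP never says that main effects will be read off the interaction model. Testing the interaction first and turning to main effects only if it is not significant fits the common practice of dropping the term and refitting, or of averaging over the other factor. Either would be valid. The term main effect names the right target. The harm requires 0/1 coding, no refit or contrast, and a simple effect reported as a main effect. The SAP gives no numeric codes or reference levels, and it uses the word dummy once, for Self-Benefit.

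The power figures rest on assumed rates. The disagreement of 14 to 59% is conditional on reaching the main-effect step; over all trials it is about 8 to 41%. With no interaction there is no bias, and the null check shows no inflation of false positives.

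All of this stands as a limit on the claim: the documents do not show that the team would report the wrong quantity. It does not remove the gap. 0/1 is the usual meaning of a dummy variable, item 5 asks for exact analyses, and the only model it gives produces simple effects. The choice between that model's coefficients and a true main effect is left open until the data are seen, which pre-registration is meant to prevent.

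**Conclusion.** The concern holds and should be fixed. Under conventional 0/1 coding, the only model named in SAP item 5 does not deliver the main effects that the same item promises, and no document states a step that would.

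The algebra is certain given that coding. The SE ratio of 1.41 needs equal openers and equal click rates across cells, but no particular open or click rate. It is approximate once those differ or covariates are added. The power losses (0.5 to 29 points, median 18, with no norm effect and no interaction) depend on the assumed open rates, click rates, odds ratios and alpha. If an interaction is missed, the coefficient can reject more or less often than the main effect, because it is a different quantity.

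**What to change.** Either of these sentences in SAP item 5 is enough:

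- *Both factors are coded -0.5/+0.5, so that their coefficients are main effects averaged over the other factor.* This replaces the dummy coding.
- *If the interaction is not significant, main effects are tested in a logistic model without the interaction term.*

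The two give nearly the same power. State that the same rule applies to the covariate-adjusted analysis. The cost is one sentence: data, sample size, randomisation and outcome do not change, and the interaction test is the same under either coding.

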Study instruments will be e-mails sent to patients, employees, and/or students through the institution that is contacting individuals about the app. E-mails will always contain basic information about COVID Alert PA and a link to download - they will also include message variations based on what the institution wants to test, including messages emphasizing data privacy and security, social norming, individual vs. community protection, and more. See attached file for a sample draft message and variation.

Group Modifications

Describe necessary changes that will or have been made to the study instruments for different groups. Groups will all receive the basic e-mail with background information on COVID Alert PA and a download link. Messages will vary between groups with message variations including emphasizing data privacy and security, social norming, individual vs. community protection, and more.

Method for Assigning Subjects to Groups

Describe how subjects will be randomized to groups.

Institutions will be responsible for selecting the group of subjects within their institution to send e-mails to, and will randomize from that group to 1 of 2 conditions. We will assist with randomization recommendations as needed.

Administration of Surveys and/or Process

Describe the approximate time and frequency for administering surveys and/or evaluations. For surveys, questionnaires and evaluations presented to groups and in settings such as high schools, focus group sessions or community treatment centers explain how the process will be administered and who will oversee the process. For instance, discuss the potential issues of having teachers and other school personnel administer instruments to minors who are students especially if the content is sensitive in nature. Describe the procedure for audio and videotaping individual interviews and/or focus groups and the storage of the tapes. For instance, if audio tape recording is to be used in a classroom setting, describe how this will be managed if individuals in the class are not participating in the study. Explain if the research involves the review of records (including public databases or registries) with identifiable

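### Does the SAP's silence on what follows a significant interaction leave the message comparisons open?

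*SAP*

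**What the plan says.** SAP item 4 sets up the factorial: "Participants will be randomly assigned to one of four conditions", crossing benefit frame (self or other) with social norm (present or absent). Item 5 specifies a logistic regression of clicking on two dummy variables and their product. The order of testing is stated: "We will examine if there is a 2 (Self-Benefit vs. Other-Benefit) x 2 (Social Norms Present vs. Social Norms absent) interaction", followed by "If there is not a significant interaction, we will examine if there is a main effect". Nothing is written for the opposite result. The covariate-adjusted runs repeat the same sequence and add no contrast. Item 8 asks "Anything else you would like to pre-register? (e.g., secondary analyses, variables collected for exploratory purposes, unusual analyses planned" and is answered NA.

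Item 6 limits the analysis set: "We will only include participants in our analysis that have opened the sent email". Item 7 gives the size: "The emails will be sent to approximately 40,000 people (10,000 per condition". Neither document states a significance level, an open rate or a click rate.

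The protocol's Analysis Plan has a single line: "Descriptive statistics, two-sample t-tests for percent download between message groups". Its section on assigning subjects says each institution "will randomize from that group to 1 of 2 conditions".

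**The concern.** The missing branch is the one in which main effects cannot answer the question. If the interaction is significant, the norm's effect on the odds of clicking depends on the frame. The test does not show in which frame the norm helps, does nothing or harms. The protocol's objective is to learn which message strategies work best, and that would then need comparisons between cells.

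Four messages form six pairs. No pair is named, no level is stated and no adjustment is mentioned. An analyst could in principle choose the comparisons after seeing the data, and report a message as better or worse than another when the two are truly equal. Carrying the protocol's t-tests over to four messages would make this look worse still.

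**Working it through.** **The plan's own figure.** 4 conditions x 10,000 = 40,000 e-mails, as item 7 states. No power calculation is given, so there is none to reproduce.

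**Number of comparisons.** C(4,2) = 6 pairs. Four change one factor (the simple effects) and two change both.

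**What the model already fixes.** Two dummies, their product and an intercept make four parameters for four cells. The model is saturated, so it returns all four cell click rates, and every simple effect is a contrast of its coefficients. With 0/1 coding, the two lower-order coefficients are themselves simple effects at the reference levels.

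**Error when all four messages are equal (two-sided 0.05 assumed).**
- Six unadjusted tests run without regard to the interaction: the studentized range tail for 4 groups at 1.96 x sqrt(2) is 20.3%. Neither document plans this analysis for this send.
- Pairs examined only after a significant interaction: P(interaction significant) = 0.050 and P(any pair significant, given that) = 0.84. The product is 0.050 x 0.84 = 0.042, or 4.2%.

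**Error when one message truly differs.** The inputs are assumptions, because the documents give none: 2,000, 3,000 or 5,000 openers per cell (20% to 50% of 10,000); 2%, 5% or 10% of openers clicking; and a relative lift of 25% or 50% in one cell. That makes 18 settings. Each was simulated with 200,000 or more binomial trials and Wald tests of log odds. Two of the four simple effects are then truly null. The rate per trial is

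P(interaction significant) x P(a null simple effect declared, given that).

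| Openers per cell / click rate / lift | Interaction significant | Null simple effect declared, given that | Per trial |
|---|---|---|---|
| 2,000 / 2% / 25% | 11.3% | 31.3% | 0.113 x 0.313 = 3.5% |
| 3,000 / 5% / 25% | 30.4% | 14.3% | 0.304 x 0.143 = 4.3% |
| 5,000 / 10% / 50% | 99.9% | about 9% | about 9% |

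Over the 18 settings the conditional rate runs from 6.4% to 31.3%. The per-trial rate runs from 3.5% to 9.0% and exceeds 5% in 5 settings. Adding the one null pair that changes both factors raises the per-trial range to 3.7% to 12.2%.

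**A ceiling that does not depend on the assumed rates.** If the interaction is real, the two norm effects differ, so at most one of them is zero. The same holds for the two benefit effects. At most 2 of the 4 simple effects can be null, and the unadjusted error is at most 2 x 0.05 = 10%. If there is no interaction, the gate itself holds the error to 5%.

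**What adjustment would buy.** Holm over four simple effects lowers the conditional rate to 3.0% to 11.5%, still above 5% in 6 of the 18 settings. In the middle row of the table it cuts power for the true norm effect, given a significant interaction, from 88% to 71%. Because at most two effects can be null, 0.025 per test after the gate is enough (2 x 0.025 = 5%). It gives 2.0% to about 4.5% per trial, with 79% power in the same setting.

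**The case for a change.** A pre-registration exists to remove choice, and item 5 asks its authors to be exact. A reader cannot tell whether two, four or six contrasts were intended, or at what level. The gate limits error only when there is no interaction. When one message differs, the other three are less well protected, and a reader who sees a significant interaction is in effect reading the conditional rate, which reaches 31%. One sentence before the send would have closed the gap.

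The omission is real, and it rests on no assumption. The conditional rates are also correct as calculated. But they are highest where a significant interaction is rare: the 31% belongs to a setting in which it occurs in 11% of trials. Over all trials, the rate stays near the nominal level through most of the range. The candidate contrasts are not open-ended either, since simple effects from the fitted model are the standard next step and the model produces them without further choices.

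The argument from the protocol's t-tests does not stand. That line belongs to a general protocol covering many institutions with two conditions each, and it refers to downloads. The SAP is specific to the Penn Medicine e-mail, has four conditions and analyses clicks.

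**Conclusion.** This is missing detail, not a rule that gives a wrong answer. The stated sequence can be carried out as written. In the branch it leaves unstated, a competent analyst would report the four cell rates and the simple effects from the same model. At an assumed two-sided 0.05 and the assumed open rates, click rates and lifts, the per-trial chance of declaring a null simple effect is about 3.5% to 9%, with a ceiling of 10% whatever those rates are.

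Whether to adjust those follow-up tests, and how, is a fair trade-off: Holm costs power, and a milder per-test level would do. Naming the contrasts would be tidier, but the send, the sample, the model and the cell estimates would be the same. The conclusion rests on the gate being respected and on simple effects being the follow-up used. An analysis that ran all six pairs regardless of the interaction would be a departure from the SAP, and the 20.3% would then apply if all four messages were equal.
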